4. SUBJECT SELECTION AND WITHDRAWAL CRITERIA

4.1. Number of Subjects

The target sample size for subjects in the treatment holiday group is at least 10 subjects and in the control group, at least 26 subjects. Each group will end recruitment when their target sample size is reached. Enrolment in this study will close when the target number of subjects in the treatment holiday and control groups has been achieved or 36 months after study start, whichever comes first. As many subjects as possible will be enrolled in the long-term discontinuation group while recruitment to the treatment holiday and control groups is ongoing and will cease when recruitment to the treatment holiday and control groups is closed or until 36 months have elapsed since study start. A target sample size of 35 subjects in the long-term discontinuation group is anticipated.

4.2. Inclusion Criteria

Specific information regarding warnings, precautions, contraindications, adverse events, and other pertinent information on the GSK investigational product or other study treatment that may impact subject eligibility is provided in the belimumab IB/IB supplement(s) and belimumab product label.

Deviations from inclusion criteria are not allowed because they can potentially jeopardize the scientific integrity of the study, regulatory acceptability or subject safety. Therefore, adherence to the criteria as specified in the protocol is essential.

Subjects eligible for enrolment in all 3 subject groups in the study must meet all of the following criteria:

1. **Belimumab therapy:** Received a minimum of 6 months therapy with belimumab 10 mg/kg in the continuation study BEL114333. Subjects in the long-term discontinuation group may additionally be recruited from continuation studies HGS1006-C1066 or LBSL99.

- 2. Age: 18 years of age at the Day 0 visit.
- 3. **Females:** A non-pregnant, non-lactating female subject is eligible to enter the study if at least one of the following conditions apply:
 - Of non-childbearing potential (i.e., women who had a hysterectomy, are postmenopausal which is defined as 1 year without menses, have both ovaries surgically removed or have current documented female sterilization procedure); or
 - Of childbearing potential (i.e., women with functional ovaries and no documented impairment of oviductal or uterine function that would cause sterility). This category includes women with oligomenorrhoea (even severe), women who are perimenopausal or have just begun to menstruate. These women must have a negative urine pregnancy test at Day 0, and agree to one of the following:
 - Complete abstinence from penile-vaginal intercourse, when this is the female's preferred and usual lifestyle, for the duration of the study for subjects in the long-term discontinuation group or until 16 weeks after the last dose of belimumab for subjects in the treatment holiday and control groups; or
 - Consistent and correct use of one of the following acceptable methods of birth control for the duration of the study for subjects in the long-term discontinuation group or until 16 weeks after the last dose of belimumab for subjects in the treatment holiday and control groups:
 - Implants of etonogestrel or levonorgestrel;
 - Estrogenic vaginal ring
 - Injectable progesterone;
 - Any intrauterine device (IUD) or intrauterine system (IUS) with a documented failure rate of less than 1% per year;
 - Oral contraceptives (either combined or progesterone only);
 - Double barrier method with vaginal spermicidal agent: Condom and an occlusive cap (cervical cap/vault or diaphragm) with a vaginal spermicidal agent (foam/gel/film/cream/suppository);
 - Percutaneous contraceptive patch;
 - Male partner who is sterile prior to the female subject's entry into the study and is the sole sexual partner for the female subject.

Note: MMF and other forms of mycophenolate affect the metabolism of oral contraceptives and may reduce their effectiveness. As such, women receiving mycophenalate who are using oral contraceptives for birth control should employ an additional method (e.g., barrier method).

4. Informed consent: Able to provide written informed consent to participate.

CONFIDENTIAL

Additional eligibility criteria for subject enrolment in the treatment holiday and control groups in the study:

- SLE: achieve the required minimal disease activity criteria defined as SELENA SLEDAI score ≤3 after a minimum of 6 months of belimumab therapy (see Appendix 1 for SELENA SLEDAI).
- 2. **SLE Treatment:** Are on a stable SLE treatment regimen consisting of any of the following medications (alone or in combination) during the 30 day screening period prior to Day 0:
 - Corticosteroids (prednisone or prednisone equivalent)
 - Other immunosuppressive or immunomodulatory agents including methotrexate, azathioprine, leflunomide, mycophenolate (including mycophenolate mofetil, mycophenolate mofetil hydrochloride, and mycophenolate sodium), mizoribine, calcineurin inhibitors (e.g., tacrolimus, cyclosporine), sirolimus, oral cyclophosphamide, 6-mercaptopurine, or thalidomide.
 - Anti-malarials (e.g., hydroxychloroquine, chloroquine, quinacrine).
 - Non-steroidal anti-inflammatory drugs (NSAIDs), including sulfasalazine.
- 3. **Complement:** C3 and C4 complement levels at or above the lower limit of normal of the central laboratory reference range.

Additional eligibility criteria for subject enrolment in the **control group** in the study:

1. **Belimumab therapy:** Agree to continue receiving 10mg/kg belimumab intravenous infusions every 4 weeks. Subjects must be able to receive the first dose of belimumab in **this study** 4 weeks (minimum of 2 weeks, maximum of 8 weeks) after the last dose in their **previous** continuation study.

Additional eligibility criteria for subject enrolment in the **long-term discontinuation group** in the study:

- 1. **Continuation studies:** Voluntarily withdrawn from continuation studies BEL114333, HGS1006-C1066, or LBSL99 and have withdrawn from belimumab therapy for no longer than 8 weeks prior to entry into this study.
- **Note:** investigators may stop, start, and/or change SLE medications and dosages as deemed necessary; yet long-term discontinuation subjects will remain on local standard of care SLE treatment therapy as determined by the physician during the study, or will need to be withdrawn.

4.3. Exclusion Criteria

Deviations from exclusion criteria are not allowed because they can potentially jeopardize the scientific integrity of the study, regulatory acceptability or subject safety. Therefore, adherence to the criteria as specified in the protocol is essential.

Subjects meeting any of the following criteria must not be enrolled in any of the 3 subject groups in the study:

- 1. Undue risk: Have developed clinical evidence of significant, unstable or uncontrolled, acute or chronic diseases not due to SLE (i.e., cardiovascular, pulmonary, hematologic, gastrointestinal, hepatic, renal, neurological, malignancy or infectious diseases), or experienced an adverse event (AE) in the belimumab continuation studies BEL114333, HGS1006-C1066, or LBSL99 studies that could, in the opinion of the principal investigator, put the subject at undue risk.
- 2. **Subject suitability:** Have developed any other medical diseases (e.g., cardiopulmonary), laboratory abnormalities, or conditions (e.g., poor venous access) that, in the opinion of the principal investigator, makes the subject unsuitable for the study.

Subjects meeting any of the following additional criteria must not be enrolled in the **control or treatment holiday groups** in the study:

- 1. **SLE:** New mild-moderate or severe flare as defined by the SLE Flare Index during the 30 day screening period prior to Day 0.
- 2. **Steroids:** Prednisone (or prednisone equivalent) greater than 20mg/day within the 30 day screening period.
- 3. New agents: Any new immunosuppressive/immunomodulatory agent, anti-malarial, or NSAID within the 30 day screening period prior to Day 0. However, any NSAID use for < 1 week is allowed.

4.4. Withdrawal Criteria

A subject may voluntarily discontinue participation in this study at any time or may be withdrawn at the discretion of the investigator. Record the primary reason for withdrawal in the electronic case report form (eCRF).

Subjects in the treatment holiday and control groups will be withdrawn from the study for:

- Pregnancy: positive urine pregnancy test.
- Clinically significant, potentially life-threatening (Grade 4) AE that in the clinical judgement of the investigator is possibly, probably or definitely related to belimumab.
- Liver chemistry abnormalities. Refer to details regarding liver chemistry abnormalities and withdrawal as specified in Section 6.4.1.

- Laboratory parameters: Demonstrate clinically important changes in laboratory parameters.
- Prohibited concurrent medication or therapy.

These subjects will complete the Week 52 Exit visit (except for dosing with belimumab) at the time of discontinuation and the16-week follow-up visit assessments at least 16 weeks after the withdrawal visit or last dose of belimumab as appropriate (see Section 6). The 6 month follow-up visit is scheduled only for those subjects in the treatment holiday or control groups.

Subjects in the long-term discontinuation group will be withdrawn from the study for:

- Pregnancy: positive urine pregnancy test.
- Laboratory parameters: Demonstrate clinically important changes in laboratory parameters.
- Have developed clinical evidence of significant, unstable or uncontrolled, acute or chronic diseases not due to SLE (i.e., cardiovascular, pulmonary, hematologic, gastrointestinal, hepatic, renal, neurological, malignancy or infectious diseases), or experienced an adverse event (AE) that could, in the opinion of the principal investigator, put the subject at undue risk.
- Have developed any other medical diseases (e.g., cardiopulmonary), laboratory abnormalities, or conditions (e.g., poor venous access) that, in the opinion of the principal investigator, makes the subject unsuitable for the study.

These subjects will complete the Week 52 visit assessments (see Section 6).

Subjects in the treatment holiday group are anticipated to be temporarily withdrawn from belimumab treatment for the initial 24 week holiday period of this study but therapy with belimumab 10 mg/kg can be reintroduced before the Week 24 visit if the subject's condition worsens or meets the definition of a severe flare as per the SLE flare index (Appendix 1). Subjects in the treatment holiday group who re-start belimumab treatment before the end of the 24-week holiday period will escape to the maintenance part of this study to receive further belimumab therapy.

The investigator must make every reasonable attempt to re-start belimumab therapy at the Week 24 visit. Any subject in the treatment holiday group who remains off-therapy with belimumab at the Week 24 visit can still be treated with belimumab from Week 28 onwards.

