5. STUDY TREATMENTS

5.1. Investigational Product and Other Study Treatment

Belimumab for intravenous (IV) infusion will be supplied in glass vials by GSK. The contents of the label will be in accordance with all applicable regulatory requirements. Detailed instructions on the preparation, administration and storage of belimumab are provided in the Pharmacy Manual. Belimumab IV solution should be prepared by a pharmacist. Reconstitute the 400 mg single use vial of belimumab with 4.8 mL sterile water for injection to yield a final concentration of belimumab 80 mg/mL. Remove an amount of normal saline from the infusion bag equivalent to the amount of belimumab to be added, add the reconstituted belimumab, and gently invert the infusion bag to mix the solution. After reconstitution and dilution in normal saline, the material is stable for up to 8 hours at 2-8°C or at room temperature. The characteristics of belimumab are summarized in Table 1.

Property	Belimumab
Formulation	Belimumab 400 mg per vial plus excipients (citric
	acid/sodium citrate/sucrose/polysorbate)
Dosage Form	Reconstituted solution
Unit dose strength	400 mg per vial (to contain 80 mg/mL when reconstituted
	with 4.8mL sterile water for injection [SWFI])
Physical description	White uniform lyophilised cake in a 20 mL vial
Manufacturer	Human Genome Sciences, Inc.
Route of administration	Intravenous

Table 1 Belimumab Characteristics

Subjects enrolled in the treatment holiday group will receive treatment with belimumab 10 mg/kg from Week 24 onwards **after** the initial 24-week treatment holiday period of the study has elapsed (see Section 3.1). At the start of the belimumab reintroduction period, subjects in the treatment holiday group will receive belimumab 10 mg/kg IV infused for over 1 hour every 28 days.

Subjects in the control group will receive belimumab 10 mg/kg IV infused for over 1 hour every 28 days from Day 0 onwards. Subjects in this group must be able to receive their first dose of belimumab on Day 0 of this study 4 weeks (minimum of 2 weeks, maximum of 8 weeks) after the last dose in the BEL114333 open-label continuation study.

Subjects in the long-term discontinuation group will not receive belimumab at any point in this study.

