6.3.1.2. Laboratory tests for SELENA SLEDAI

A strong correlation has been demonstrated between the protein content of a 24-hour urine collection and the protein:creatinine ratio in a single urine sample [Ginsberg, 1983; Ruggenenti, 1998; Clinical Practice Guidelines for Chronic Kidney Disease, 2002; Price, 2005]. For this reason, spot urine protein:creatinine ratio will be used for determining proteinuria in this study for the SELENA SLEDAI disease activity indices.

Measurement of creatinine clearance (CrCl)/glomerular filtration rate (GFR) using timed (for example, 24-hour) urine collections is time consuming and error prone and has consistently been shown to be no more, and often less, reliable than serum creatinine based equations for the estimation of GFR [Clinical Practice Guidelines for Chronic Kidney Disease, 2002]. Therefore, GFR estimated by the Cockroft-Gault formula will be used as was done in the Phase II trial of belimumab (LBSL02) and Phase III.

Cockroft-Gault Equation [Cockcroft, 1976]

$$Cl_{cr}(mL/\min) = \frac{(140 - age(yrs))xweight(kg)}{72xserumcreatinine(mg/dL)} \times 0.85 \text{ if female}$$

Values outside the reference laboratory normal range that require the investigator's assessment of relationship to SLE:

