The following are required for subjects with ALT $\ge 3xULN$ and bilirubin $\ge 2xULN$ (>35% direct) or ALT $\ge 3xULN$ and INR>1.5, if INR measured; but are optional for other abnormal liver chemistries:

- Anti-nuclear antibody, anti-smooth muscle antibody, and Type 1 anti-liver kidney microsomal antibodies, and quantitative total immunoglobulin G (IgG or gamma globulins).
- Serum acetaminophen adduct HPLC assay (quantifies potential acetaminophen contribution to liver injury in subjects with definite or likely acetaminophen use in the preceding week [James, 2009]). **NOTE: not required in China.**
- Liver imaging (ultrasound, magnetic resonance, or computerized tomography) to evaluate liver disease.

For long-term discontinuation group subjects found to have met the liver stopping criteria without receiving belimumab, investigators will apply the withdrawal criteria in Section 4.4.

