6.4.3. Laboratory and Other Safety Assessment Abnormalities Reported as AEs and SAEs

Any abnormal laboratory test results (haematology, clinical chemistry, or urinalysis) or other safety assessments (e.g., ECGs, radiological scans, vital signs measurements), including those that worsen from baseline, and felt to be clinically significant in the medical and scientific judgement of the investigator are to be recorded as AEs or SAEs. However, any clinically significant safety assessments that are associated with the underlying disease, unless judged by the investigator to be more severe than expected for the subject's condition, are **not** to be reported as AEs or SAEs.

Investigators will be required to fill out event specific data collection tools for the following AEs and SAEs, including but not limited to:

- Myocardial infarction/unstable angina
- Congestive heart failure
- Arrhythmias
- Valvulopathy
- Pulmonary hypertension
- Cerebrovascular events/stroke and transient ischemic attack
- Peripheral arterial thrombosis
- Deep Venous Thrombosis
- Revascularization
- Hypersensitivity reactions

- Herpes zoster
- Malignancies

This information should be recorded within one week of when the AE/SAE(s) are first reported.

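### Protocol 4.4 withdraws long-term discontinuation subjects for laboratory worsening without exempting SLE, and LOCF then records those who leave before Week 24 at or below parent baseline as no rebound

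*Protocol*

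**What the plan says.** **Withdrawal rule.** Protocol 4.4 lists mandatory withdrawal criteria for the LTD group. One reads "Laboratory parameters: Demonstrate clinically important changes in laboratory parameters". It gives no parameter list, no threshold and no exception for lupus. The next criterion in the list covers acute or chronic disease, but only where SLE is not the cause. The fourth covers "laboratory abnormalities, or conditions (e.g., poor venous access) that, in the opinion of the principal investigator, makes the subject unsuitable for the study", again with no SLE exception. The list for the treatment holiday and control groups contains the same laboratory criterion.

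**Role of the LTD group.** Protocol 3.1 says the group is used to assess rebound and admits any level of disease activity. Protocol 5.1 states: "Subjects in the long-term discontinuation group will not receive belimumab at any point in this study". A note in Protocol 4.2 says that "investigators may stop, start, and/or change SLE medications and dosages as deemed necessary". For LTD subjects who meet the liver stopping criteria, Protocol 6.4.1 says "investigators will apply the withdrawal criteria in Section 4.4", so the criterion also has a safety role unrelated to SLE.

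**Rebound analysis.** SAP 7.2.1.3 defines rebound as a SELENA SLEDAI score in the first 24 weeks above the parent-study baseline. SAP 7.2.2.3 reports it by visit and at any time to Week 24, and 7.2.3 repeats it by Day 0 score (≤3, >3). SAP 7.2.4.2 fills missing scores by LOCF, but not across the holiday and re-start phases. SAP 13.3.3 slots Exit visits to planned visits. Table 2.6 is marked as a headline result.

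**The concern.** An LTD subject has no study drug to stop, and background SLE treatment may be changed freely. Withdrawing such a subject for an SLE laboratory change therefore ends observation of the outcome the group was set up to measure. The LTD group has no follow-up visits after Exit (Protocol 6). Worsening lupus makes both withdrawal and later rebound more likely, so the missing scores are related to the outcome. LOCF fills them with the last observed score, which for these subjects means no rebound. Any resulting error is in the reassuring direction. In a study with no hypothesis test, the reported proportion is itself the result, and rebound is part of the stated rationale (Protocol 1.2).

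**Working it through.** The plan gives no figure for this point to reproduce. The enrolled numbers in SAP 2.3 agree: 12 + 29 + 39 = 80.

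**1. Path of a subject withdrawn before Week 24.**
- The Exit assessments include SELENA SLEDAI (Protocol 4.4 and Table 2), and the visit is slotted by study day (SAP 13.3.3).
- If the Exit score or an earlier score exceeds parent baseline, rebound is counted.
- If not, the last score is carried forward to Week 24 and the subject counts as no rebound.
- This is wrong only if the subject would have crossed between Exit and Week 24.

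**2. How far laboratory disease can worsen below the threshold.**
- SAP 13.6.3 names eight laboratory items: four renal at 4 points, two immunologic at 2 and two hematologic at 1. Total: 4×4 + 2×2 + 2×1 = 22 of 105 points.
- The only parent entry score given is ≥8, for BEL113750 (Protocol Appendix 7, Section 3.2). At parent baseline 8, rebound needs at least 9.
- Example from a Day 0 score of 0: new proteinuria 4 + low complement 2 + raised anti-dsDNA 2 = 8, which is not rebound.
- Pairs of laboratory items totalling 8 or less: 28 of 28 (maximum 4 + 4).
- Triples: one renal item plus two of the other four gives 4 × 6 = 24; no renal item gives 4; so 28 of 56.

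These counts show that substantial SLE laboratory change can occur before the threshold is crossed. They do not estimate bias.

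**3. Weight of one subject.**
- LTD: 1/39 = 2.6 points; two subjects, 2/39 = 5.1 points.
- Within a Day 0 stratum, if the strata held 13 and 26 subjects (assumed; sizes are not given): 1/13 = 7.7 and 1/26 = 3.8 points.
- Treatment holiday: 1/12 = 8.3 points.
- Illustration, assuming 2 observed LTD rebounds and k subjects lost before Week 24 without one. LOCF gives 2/39 = 5.1% whatever k is. The worst case is (2 + k)/39:

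| k (assumed) | Worst case |
|---|---|
| 1 | 7.7% |
| 2 | 10.3% |
| 3 | 12.8% |
| 5 | 17.9% |

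**4. Treatment holiday group.** It is off belimumab to Week 24, is named in the rebound endpoint (Protocol 6.1.2), has the same laboratory criterion, and uses LOCF within the holiday phase. SAP 13.4.1.1 assesses rebound only up to Week 24 or re-start, so a subject who escapes early also leaves rebound observation.

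**5. Other endpoints.** SAP 7.2.4.1 says withdrawal counts as an SFI flare and is headed to include first severe flare. It also refers to 7.1.4, which censors withdrawals. SAP Appendix 7 censors them for time to SFI flare and imputes a flare only for the number of flares. The documents conflict for severe flare.

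**The case against.** The strongest reply is that this is an ordinary safety stop. The laboratory criterion names no judge; that the investigator decides is inferred from the opening of 4.4 and from the fourth criterion. Nothing says that lupus serology was meant to trigger it. The protocol admits LTD subjects at any activity level, and Protocol 6.4.3 treats disease-related laboratory findings separately from adverse events. An investigator might never have applied the criterion to SLE changes. Exit also captures a rebound already present. All of this stands, and it is why no size of bias can be claimed. It does not remove the problem: the text makes withdrawal mandatory, the SLE limit appears in the neighbouring criterion but not here, and no other section supplies it.

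Four stronger readings are tempting but not supported:
- *Rebound is understated by a known amount.* The documents do not say how many subjects were withdrawn on this ground, or whether any would have crossed later.
- *Reclassifying only SLE-related laboratory withdrawals would bound the effect.* It would not. LOCF treats every withdrawal before Week 24 alike, whatever the reason.
- *SLE attribution is already on record for these withdrawals.* The main text of Protocol 6.3.1.2 is an unfinished sentence ("Values outside the reference laboratory normal range that require the investigator's assessment of relationship to SLE"), completed only in the China text of Appendix 7. No eCRF field linking a laboratory withdrawal to SLE is shown.
- *The severe-flare analysis compensates by counting withdrawal as an event.* The SAP contradicts itself there, so no such protection should be claimed.

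**Conclusion.** The point holds in limited form. A stated rule lets worsening lupus end observation of rebound, and LOCF then resolves the unseen weeks as no rebound. The loss is confined to crossings after Exit and before Week 24. It concerns the LTD group chiefly and the treatment holiday group during the holiday phase. Each LTD subject is worth 2.6 percentage points (n = 39); the number affected is unknown and may be zero. The 8-point example assumes a Day 0 score of 0 and the minimum entry score of one parent study. Results are descriptive and rebound is a secondary endpoint, so this is a cheap improvement. It does not invalidate the study.

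**What to change.** **Protocol 4.4, LTD group.**
- Add *not due to SLE in the investigator's judgement* to the laboratory criterion.
- Add the same qualifier to laboratory abnormalities in the fourth criterion, except where continuing would put the subject at risk.
- State that subjects with SLE-related changes stay on scheduled visits to Week 52.
- Keep the stops for non-SLE laboratory changes and for liver events.

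This costs a few words and uses visits already planned, though some subjects stay longer under observation. It is probably too late for this study: SAP 2.3 reports 80 enrolled and 5.3.1 refers to Last Patient Last Visit. It would serve a successor.

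**SAP Table 2.6.** Beside the LOCF row, add a worst-case sensitivity row for LTD and, separately, for treatment holiday. Count as rebound every subject who leaves rebound observation before Week 24 without an observed rebound: withdrawals for any reason, plus holiday escapes. List the recorded withdrawal reasons alongside (Listing 5 already holds them).

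This is a true upper limit for that dropout, needs no SLE-attribution field and uses data already collected. If no one qualifies, the two rows agree and the question is closed. The drawback is that the bound may be wide, and it is a limit, not an estimate; the table should say so.
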